15. MEASUREMENT OF EFFECT

15.1 Anti-Tumor Effect

Patients will be evaluated for anti-tumor effect by follow-up imaging (CT and PET-CT imaging) as outlined above. Initial follow-up scans post-treatment will be compared to the patient's baseline scan, defined as the scan prior and closest to the date of initiating chemotherapy.

15.1.1 Definitions

Patients will be evaluable for toxicity and evaluable for objective response at follow-up intervals specified in the Calendar above (Section 14).

15.1.2 Disease Parameters

Pancreatic tumor response will be based upon standard radiographic criteria for the treated lesion and will be prospectively recorded in the combined JHU secure database. Radiographic response of the pancreatic tumor by diagnostic CT scans will be defined according to RECIST criteria as described below:

CR = complete disappearance of index lesion
PR = at least 30% decrease in the longest diameter of the index lesion
PD = more than 20% increase in the longest diameter of the index lesion
SD = does not meet criteria for PR or PD

Pancreatic tumor response will also be assessed by FDG-PET scans (when available) according to the following criteria:

CR = target lesion becomes photopenic or standardized uptake value (SUV) ratio of tumor/liver less than or equal to 1
PR = decrease in SUV ratio of tumor/liver (at least 30%)
PD = increase in SUV ratio of tumor/liver (at least 20%)
SD = no significant change in SUV ratio of tumor/liver

Definitions of Progression

Local tumor progression will be defined as $\geq 20\%$ increased size on follow-up CT scan as compared to baseline CT (scan prior and closest to the date of initiating chemotherapy).

Distant progression will be defined as any tumor found outside of the pancreas on CT scan. Local and/or distant progression by both PET and CT scan will be recorded separately. FDG-PET is not required but highly recommended as a complementary method for determining response. We will also determine PET response with the new PERCIST criteria as reported by Wahl et al. (J Nuc Med 2009; 50:122S-150S).

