1.2. Secondary Objectives

- To compare metastasis free survival for pancreatic patients following chemotherapy +/- SBRT.
- To compare the one year progression-free survival for patients treated with mFFX +/- SBRT.
- To determine the overall survival for patients treated with mFFX +/- SBRT.
- To determine local progression-free survival for patients treated with mFFX +/- SBRT.
- To evaluate acute (within 3 months of treatment) grade 2 or greater gastritis, fistula, enteritis, or ulcer and any other grade 3-4 gastrointestinal toxicity within 3 months of treatment.
- To evaluate the utility of FDG-PET for treatment planning and estimation of progression free survival.
- To identify new biomarkers in pancreatic cancer.
- To evaluate the quality of life before and after therapy for patients treated with mFFX +/- SBRT.

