6. RADIATION TREATMENT PLANNING AND SBRT ADMINISTRATION

6.1 Pre-SBRT Tests, Procedures, and Planning

The following will be completed **prior to SBRT**:

- a) Consultation with medical history and physical examination.
- b) Pathology with report confirming malignancy.
- c) Labs: CBC with differential, CMP (Comprehensive Metabolic Panel) and CA199. CEA is optional. Additionally, up to 20ml of additional blood may be drawn for research purposes (study bloods may also be collected in follow-up visits). For specific information regarding collection and processing, see Section 12.1 Laboratory Correlative Studies.
- d) Seed placement: Gold fiducial seed placement percutaneously, intraoperatively, or under endoscopic ultrasound guidance, which may be performed prior to study enrollment. In some patients, an optional additional core biopsy may be obtained for research purposes if consent is provided by the patient, and may be done at the time of fiducial implantation (See Section 12.1, Laboratory Correlative Studies) or in a separate procedure. For patients who are planned to be treated with active breathing coordinator (ABC) or 4D kV CBCT IGRT, fiducial seed placement is optional.
- e) Scans: CT or MR. PET/CT scan is recommended though not required.
- f) Signed informed consent.
- g) Negative Pregnancy Test (urine or serum) for females of childbearing potential OR menopausal as defined in Appendix III – Definition of Menopausal Status.
- h) Eligibility confirmation.
- i) Study registration and randomization.
- j) Quality of Life Survey: Baseline collection of EORTC QLQ C-30/ PAN26 QOL.

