17.4 Plan of Analysis

Demographic and clinical characteristics of patients and the characteristics of treated lesions (volume, location, and modality) will be summarized by means, medians, standard deviations, ranges and proportions as applicable.

Time to event outcomes (overall survival, metastasis free survival, and progression free survival) will be summarized using Kaplan-Meier curves and medians with 95% confidence intervals calculated using Greenwood's formula. Cox proportional hazards models will be used to compare treatment groups and to assess risk factors (e.g. biologic markers and PET volume). The effect of site will be tested in the Cox models; the effect of whether or not the patients received Leucovorin will also be tested in the Cox models. The level of response (and other categorical outcomes) will be tabulated at each follow-up interval. Logistic regression and Cox models will be used to assess the proportion with a response category depending upon the level of censoring prior to the annual visit.

The measurements of the volume of the pancreatic tumors based upon CT and PET-CT scans will be compared using paired t-tests or Wilcoxon signed-rank tests as appropriate. The agreement between pancreatic tumor measurements will be compared among the three institutions using correlation coefficients, percentage agreement, and inter-correlation coefficients.

Quality of life outcomes will be assessed at each time interval and compared using the recommended guidelines from the module. Differences in QOL for the two treatment groups will be explored using a repeated measures model in order to account for the within-patient correlation. Special interest will be placed on exploring the aspects of QOL which are known to be impacted by SBRT.

At this time all research on biomarkers for disease progression is exploratory. The goal is to potentially identify biomarkers that are associated with disease progression. Should any biomarkers be identified, their impact on the time to event outcomes will be summarized using Kaplan Meier curves and they will be tested using Cox proportional hazards models.

Quality of life at each interval will be calculated and compared using the recommended guidelines from the module (available by E-mail: [contact]). Efficacy outcomes with repeated measurements over time (e.g. quality of life) will be analyzed using a generalized estimating equation (GEE) approach to account for within-patient

correlation.

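### PET complete response is set by an absolute ratio with no baseline condition, so an unchanged low-uptake lesion scores CR and some scans score CR and PD together

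*Combined protocol and SAP*

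**What the plan says.** Section 15.1.2 gives four PET categories, all but part of CR built on the tumor/liver SUV ratio:

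- Complete response: "CR = target lesion becomes photopenic or standardized uptake value (SUV) ratio of tumor/liver less than or equal to 1".
- Partial response: "PR = decrease in SUV ratio of tumor/liver (at least 30" per cent).
- Progression: "PD = increase in SUV ratio of tumor/liver (at least 20" per cent).
- Stable disease: "SD = no significant change in SUV ratio of tumor/liver".

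The comparison scan is set in Section 15.1, which covers both CT and PET-CT, as the one "defined as the scan prior and closest to the date of initiating chemotherapy". No minimum uptake is required of it. PET is optional: Section 6.1 says "PET/CT scan is recommended though not required", and the Study Calendar (Section 14, note e) recommends it only at screening and, if a single follow-up PET is possible, at 3 months.

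Section 15.1.2 adds that PERCIST will be determined too, without saying which reading governs, and that PET and CT progression are recorded separately. Section 1.2 lists as a secondary objective "To evaluate the utility of FDG-PET for treatment planning and estimation of progression free survival". Section 17.4 tabulates level of response at each follow-up interval.

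**The concern.** CR is partly an absolute threshold, while PR and PD are relative changes. Rules of the two kinds can be combined safely only if the absolute one is tied to a starting point above the threshold, or if the categories are ranked. Section 15.1.2 does neither. The CT rules in the same section make SD whatever is not PR or PD. The PET rules leave SD as an unquantified absence of significant change, so SD does not exclude CR.

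At stake is whether each PET scan has one code. Where the rule gives two codes, or gives CR to a lesion that has not changed, someone must choose a code after seeing the data. That choice then enters the PET response table and the PET progression record, and through them any reading of the FDG-PET objective.

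**Working it through.** The plan attaches no figure to this rule, so there is nothing to reproduce. The check applies the written rules to pairs of ratios.

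**Inputs (Section 15.1.2).** Let b be the baseline ratio and f the follow-up ratio, with change = f/b − 1. CR if f ≤ 1; PR if change ≤ −30%; PD if change ≥ +20%. SD is taken as neither PR nor PD. That is an assumption, because the text does not quantify it. The photopenic limb is taken as not met. The baseline values are illustrations; the documents give none.

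**When CR and PD coincide.** PD needs f ≥ 1.2b and CR needs f ≤ 1. Both hold for some f only if 1.2b ≤ 1, that is b ≤ 1/1.2 = 0.833. Between 0.833 and 1 a 20% rise takes the ratio above 1, so only PD applies.

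**When an unchanged lesion is CR.** With f = b, CR holds whenever b ≤ 1.

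**Examples.** The last column applies the change proposed below, with CR ranked above PR.

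| Baseline | Follow-up | Change | Codes met as written | Code after the fix |
|---|---|---|---|---|
| 0.90 | 0.90 | 0% | CR and SD | SD |
| 0.90 | 1.00 | +11% | CR and SD | SD |
| 0.80 | 0.96 | +20% | CR and PD | PD |
| 0.70 | 0.90 | +29% | CR and PD | PD |
| 0.50 | 0.90 | +80% | CR and PD | PD |
| 0.90 | 1.08 | +20% | PD | PD |
| 0.90 | 3.00 | +233% | PD | PD |
| 1.05 | 0.99 | −6% | CR and SD | CR |
| 2.00 | 1.00 | −50% | CR and PR | CR |

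**Does the fix remove the conflict?** If the ratio limb of CR requires b > 1, a rise of at least 20% gives f > 1.2, which cannot be ≤ 1. So CR by ratio and PD can no longer coincide. Baselines of 1 or less can still be scored PD, PR or SD.

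**The case against.** The strongest reply is grammatical. The verb *becomes* might govern both limbs of the CR definition, so that CR means a move from above 1 to 1 or below. On that reading an unchanged lesion at 0.90 is not CR, and neither is 0.70 to 0.90. It is a sensible intention, but the text does not state it for the ratio limb. If it is what was meant, the fix simply writes it down.

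The second reply is that little depends on this rule. PET is optional and complementary, PERCIST is a second reading, and local and distant progression are defined on CT. That stands and limits the weight of the point. It does not remove it: PERCIST is additional rather than a replacement, and PET progression is still recorded.

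Three stronger readings are tempting, and the documents do not support them:

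- *Low baselines must be common because enrolment is allowed after up to four cycles of mFFX.* Section 15.1.3 does call the baseline PET pre-study, but Section 15.1 defines the baseline scan as one before chemotherapy. A scan after mFFX is not the defined baseline.
- *The error distorts the modelled link between PET response and PFS.* No such model is specified. Section 17.4 says "Logistic regression and Cox models will be used to assess the proportion with a response category", but the sentence goes on to tie this to censoring before the annual visit, and the calendar recommends PET only at screening and 3 months. The PET covariate that 17.4 names for the Cox models is volume, not response category. Section 17.1.2 leaves the FDG-PET objective out of its endpoint list.
- *CR should need a 30% fall, since below a baseline of 1/0.7 = 1.43 every PR is also CR.* That follows from choosing an absolute target. CT CR in the same section is absolute as well. A fall from 1.05 to 0.99 scoring CR is a design choice, not a contradiction.

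**Conclusion.** The point holds in a limited form. As written, the ratio limb of PET CR codes any unchanged lesion with a baseline of 1 or less as CR (and SD). It gives opposite codes, CR and PD, to a lesion with a baseline of 0.833 or less that rises by at least 20% and stays at or below 1. These results follow from the written rules by arithmetic. The CR and SD overlap also uses the assumption that an unchanged ratio counts as SD.

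How many patients are affected cannot be stated. It depends on the distribution of baseline ratios and on the measurement error of the ratio, and the documents give neither. The number could be close to zero. A reader should therefore not infer that the PET CR rate mainly reflects baseline uptake, or that PFS results are at risk. What is affected is the PET response tabulation, the PET progression record and the secondary FDG-PET objective.

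**What to change.** In Section 15.1.2:

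1. Keep the photopenic limb of CR. Apply the limb for a ratio of 1 or less only when the baseline ratio exceeds 1.
2. Score a rise of at least 20% as PD in every case, including baselines of 1 or less. Say in the same sentence that CR outranks PR when both are met.
3. Define PET SD as not meeting CR, PR or PD, in the way the CT rule already does for PR and PD.
4. State whether the ratio rule or PERCIST governs the PET analysis.

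Lesions with a baseline of 1 or less should not be coded as not evaluable across the board. That would discard real PET progression, such as 0.90 to 3.00, which the current rule codes correctly.

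The cost is a few sentences and no new scans. The PET CR rate may be slightly lower, because unchanged low-uptake lesions no longer count.

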5. INDUCTION CHEMOTHERAPY

5.1 mFOLFIRINOX

After study enrollment, patients will receive (or continue with) mFOLFIRINOX (omission of bolus 5FU) as outlined below, allowing for modifications of dose and schedule as per clinical judgment of patient's treating physician. For patients who have received FOLFIRINOX chemotherapy including a 5FU bolus prior to study entry, once consent is signed, the 5FU bolus must be omitted. Because of its improved safety profile without sacrificing efficacy, mFOLFIRINOX is commonly administered in the treatment of pancreatic cancer (31). Modified FOLFIRINOX regimen with improved safety and maintained efficacy in pancreatic adenocarcinoma. *Pancreas* 2013 Nov 42(8):1311-5.

mFOLFIRINOX may be administered in a community practice setting as long as the treating oncologist assumes responsibility for all reporting and follow-up requirements.

Prophylactic growth factors may be administered at any time before, during, or after chemotherapy cycles. It is recommended that the patient be evaluated at one of the participating centers every 3-6 months. As standard practices are changing and Leucovorin is not widely used, we will allow the omission of this drug during both induction and treatment phases of the study.

mFOLFIRINOX to complete a total of 4 cycles, (1 cycle = 14 days)

- Oxaliplatin 85 mg/m² IV over 2 hours on Day 1, followed by
 - Irinotecan 180 mg/m² IV over 90 minutes on Day 1, followed by
 - Leucovorin* 400 mg/m² IV over 2 hours on Day 1, followed by
 - 5FU** 2,400 mg/m² IV over 46 – 48 hours
- *Leucovorin may be administered concurrently with the last 30 minutes of oxaliplatin, and the entire 90 minutes of irinotecan.
- **5FU is administered via infusion only; there is no bolus injection of 5FU.

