5.2 Restaging Following mFOLFIRINOX

After induction chemotherapy (up to 4 cycles), patients will have a CT scan for re-staging. Re-staging scans should be scheduled within 2 weeks following completion of induction mFOLFIRINOX. To allow for scheduling complications, outside sites may perform the simulation (SIM) scan during the final cycle of chemotherapy up to 4 weeks prior to start of treatment. If the subjects are randomized to the SBRT arm and the SIM was more than 4 weeks prior to treatment start date, a re-SIM will be performed to ensure that the plan is still appropriate for tumor treatment.

- If there is radiological or clinical evidence of disease progression, patient will not continue with the randomized portion of this study, but should be treated according to treating physician's discretion. (Based upon the study by Conroy *et al*, the progression-free survival at 3 months is estimated to be 75%; therefore the number of patients evaluated for the protocol and ultimately enrolled will be adjusted accordingly.) These patients will continue to be followed as part of the study.
- If a patient has radiologically responding or stable disease, s/he may proceed with randomization as described in the following section. Patients may undergo surgical resection at any time if clinically appropriate after surgical evaluation.

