15.1.5 Progression-Free Survival (or other time-to-event parameters)

The criteria for time to progression and progression-free survival (PFS) will be the time from randomization to documented progression or death. Individuals will be censored at the date of last evaluation for progression if neither event is observed. Overall survival will be defined as time from randomization until death from any cause. Participants will be censored at the date of last contact if the date of death is not observed. Local PFS will be the duration from randomization to local progression or death if death occurs before local progression. Metastasis free survival will be the duration from randomization to metastasis or death from any cause, if death occurs before metastasis. Individuals will be censored at the time of the last evaluation for local or distant progression, respectively, if neither progression nor death is observed.

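### Local progression after randomization is judged against the pre-induction scan, so size change before the PFS clock starts sets each patient's threshold and probably weakens the measured SBRT effect

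*Combined protocol and SAP*

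**What the plan says.** Section 15.1.2 defines local progression as a size increase of at least 20% at follow-up CT "as compared to baseline CT (scan prior and closest to the date of initiating chemotherapy". Section 15.1 uses the same reference for the initial follow-up scans, which are compared with the "baseline scan, defined as the scan prior and closest to the date of initiating chemotherapy". No section names another reference for later scans.

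The clock starts elsewhere. Section 15.1.5 says that "progression-free survival (PFS) will be the time from randomization to documented progression or death", and local PFS has the same origin. Randomization comes after induction: section 5.1 gives "mFOLFIRINOX to complete a total of 4 cycles, (1 cycle = 14 days", about 8 weeks in full. Section 5.2 then adds: "After induction chemotherapy (up to 4 cycles), patients will have a CT scan for re-staging". On timing it says: "Re-staging scans should be scheduled within 2 weeks following completion of induction mFOLFIRINOX". Only patients with responding or stable disease go on to randomization.

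Stratification is by ECOG status only (17.4.1), and the covariates named for the Cox models (17.4) do not include response to induction.

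**The concern.** SBRT can act only on growth after randomization, yet whether that growth counts depends on what the tumour did beforehand. A patient whose tumour shrank well in induction must regrow past the original size and a further 20%, and may have distant progression or die first. A patient whose tumour grew slightly, but still counts as stable, can be called progressed at the first follow-up scan on a change within ordinary measurement variation, in either arm. Neither patient tells us much about local control. The primary endpoint and the secondary local PFS endpoint may therefore be less sensitive to the effect the trial was built to detect.

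**Working it through.** **1. The plan's own figure.** Inputs from 17.3.2 and 17.5.2: 86 patients per arm, medians of 6 and 10.2 months, exponential survival, 60 months of accrual, at least 12 months of follow-up, two-sided alpha 0.05. With uniform accrual, expected events are 82.9 + 76.8 = 159.7 (plan: 83 + 77 = 160). The hazard ratio is 6/10.2 = 0.588. Power at 160 events is 91.9% (Schoenfeld) or 90.6% (Freedman), against 91% stated. The plan's figure reproduces.

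**2. Growth needed after randomization.** If size changes by a fraction c during induction, growth needed from the re-staging size is 1.20/(1 + c) − 1.

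| Change in induction | Calculation | Growth needed |
|---|---|---|
| −30% | 1.20/0.70 − 1 | 71.4% |
| −20% | 1.20/0.80 − 1 | 50.0% |
| −10% | 1.20/0.90 − 1 | 33.3% |
| 0% | 1.20/1.00 − 1 | 20.0% |
| +10% | 1.20/1.10 − 1 | 9.1% |
| +15% | 1.20/1.15 − 1 | 4.3% |
| +19% | 1.20/1.19 − 1 | 0.8% |

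For an assumed 40 mm tumour the event size is 48 mm. After 30% shrinkage it starts from 28 mm and must grow 20 mm; after 19% growth it starts from 47.6 mm and must grow 0.4 mm.

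**3. Effect on the hazard ratio (illustration only).** The documents give no distribution of size change in induction, no local growth rate and no local share of PFS events. Assumptions:
- log growth rate with the median shown below and log SD 0.6
- SBRT multiplies growth by the factor shown, with no delay
- scans every 3 months
- distant progression or death exponential and equal in both arms
- induction change normal, with mean from −25% to +5% and SD of 10 to 20 points, truncated below +20%

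The SBRT factor is tuned so that the re-staging reference gives the design hazard ratio. Power is at 160 events.

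| Growth per month | Distant median (months) | SBRT factor | HR (power), re-staging reference | HR (power), pre-chemotherapy reference |
|---|---|---|---|---|
| 0.03 | 12 | 0.49 | 0.59 (92%) | 0.67–0.75 (73%–45%) |
| 0.04 | 9 | 0.46 | 0.59 (92%) | 0.67–0.75 (73%–46%) |
| 0.04 | 12 | 0.51 | 0.59 (92%) | 0.66–0.73 (75%–50%) |
| 0.06 | 12 | 0.51 | 0.59 (92%) | 0.63–0.71 (83%–58%) |

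In the first three rows the control median under the re-staging reference is 5.4 to 6.0 months, near the planned 6. In the fourth it is 3.0 months; there the current rule gives a median of about 5 to 6 months when tumours shrink on average.

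**4. Where it vanishes or reverses.** SBRT factor 0.3, distant median 12 months, SBRT effect delayed 2 months, SD 15 points:
- growth 0.06 per month, mean shrinkage 12%: 0.652 (re-staging) against 0.647 (pre-chemotherapy), no difference
- growth 0.10 per month, mean shrinkage 20%: 0.81 against 0.65, a reversal

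Without delay, growth 0.20 per month, SBRT factor 0.5, distant median 9 months and mean shrinkage 25% gives 0.86 against 0.67.

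A separate grid of 24 settings (SBRT halving growth, delay 0 or 2 months, growth 2–10% per month) showed attenuation in 17. These included all 12 with growth of 2–3% per month. The 7 reversals, some trivial, all had growth of at least 5% per month and a re-staging control median below 4 months.

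**The case against.** The threshold is fixed before randomization and is balanced between arms in expectation. A reader might infer that the rule biases the comparison or inflates the type I error; it does neither. That part of the objection stands in full, but it does not answer the loss of sensitivity.

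A reader might also infer that noise in a threshold always pulls the hazard ratio toward 1, or that power has fallen to a particular figure. The documents do not support this. Attenuation is a result of the model, not a property of the rule. Sections 5.3 and 6.2 allow up to 8 weeks between induction and SBRT, so a delayed effect is realistic, and with delay and fast growth the sign can change. In some of the reversals the control median under the current rule was still 6 months, so the planned median does not rule them out.

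The illustration also gives both arms the same distant failure rate, although section 2.3 suggests SBRT might reduce distant seeding. With an assumed distant hazard ratio of 0.6, or with SBRT suppressing 90% of local growth, power is about 97% to 100% under either reference. Finally, distant disease, death (15.1.2, 15.1.5) and clinical progression (7.4) count toward PFS and do not use the 20% rule. All this limits the size of the claim. It does not explain why a threshold running from under 1% to over 70% is preferable.

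**Conclusion.** The mismatch is in the text and nothing elsewhere corrects it: the reference scan precedes the time origin by the whole of induction, and the growth that counts as an event ranges from 0.8% to 71% for induction changes between +19% and −30%. The consequences are added noise, marked regrowth that can go uncounted, and a probable weakening of the measured SBRT effect on PFS and local PFS.

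Under the assumed inputs, a hazard ratio of about 0.59 becomes 0.63 to 0.75, or 0.66 to 0.75 where the re-staging control median is near the planned 6 months. These are illustrations resting on growth rate, induction change, delay of effect and the local share of events, none of which the documents give. The direction is probable, not certain. It would be wrong to conclude that the 91% power is miscalculated: it follows correctly from the stated medians. The point is a cheap improvement to a primary endpoint definition, not a flaw that invalidates the comparison.

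**What to change.** In 15.1.5, for PFS and local PFS, define local progression after randomization as an increase of at least 20% over the re-staging CT required in 5.2. Keep the pre-chemotherapy reference as a prespecified sensitivity analysis for both endpoints. Reconcile the two thresholds in 15.1.2: the PD line needs more than 20%, the local-progression line 20% or more, so a tumour exactly 20% larger is stable by one and progressed by the other. Make the change before outcomes are compared by arm.

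This alters an endpoint definition and no treatment rule. It needs no extra scan: the re-staging CT is already mandatory, section 12.2.1 collects it, and the independent radiology review in 15.1.6 can read against both references.

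The costs are these:
- Patients who shrank are called progressed earlier in both arms, so median PFS may look shorter.
- Patients who grew 15% to 19% in induction are called only at 1.15 × 1.20 = 1.38 to 1.19 × 1.20 = 1.43 times their pre-treatment size.
- A fixed re-staging reference still does not count regrowth from a smaller size reached later.
- Section 7.5 takes progression for removal from 15.1.2 and then follows removed patients for survival only. The amendment must say how a patient removed before meeting the new endpoint rule is counted.

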3.2 Exclusion Criteria

- Children/Age<18 (rarely occurs in this age group)
- Metastatic disease.
- Prior radiotherapy to the upper abdomen/liver.
- Patients who have received chemotherapy for pancreatic cancer, other than up to 4 cycles of mFOLFIRINOX as noted above.
- Uncontrolled illness including, but not limited to, ongoing or active infection (or infections requiring systemic antibiotic treatment), symptomatic congestive heart failure, unstable angina pectoris, cardiac arrhythmia, or psychiatric illness/social situations that would limit compliance with study requirements.
- Any concurrent malignancy other than non-melanoma skin cancer, non-invasive bladder cancer, or carcinoma in situ of the cervix. Patients with a previous malignancy without evidence of disease for > 5 years will be allowed to enter the trial.
- Pregnant and breastfeeding women are excluded; as well as women of child-bearing potential who are unwilling or unable to use an acceptable method of birth control (hormonal or barrier method of birth control; abstinence) to avoid pregnancy for the duration of the study. Male subjects must also agree to use effective contraception for the same period as above. Should a woman become pregnant or suspect she is pregnant while participating in this study, she should inform her treating physician immediately.
- Women who are not post-menopausal (as defined in Appendix III) and have a positive urine or serum pregnancy test or refuse to take a pregnancy test.

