15.1.3 Methods for Evaluation of Measurable Disease

Pancreas protocol CT or chest abdomen pelvis CT (biphasic imaging, 1.25 mm cuts) will be obtained at follow-up intervals as described in Section 14. Study Calendar. PET-CT scans should be done at baseline (pre-study) and repeated if possible at the 3-month follow-up.

Standard radiographic criteria will be utilized for non-target lesions. Any disease outside of the pancreas will be considered metastatic disease. If possible a biopsy should be obtained to confirm metastasis.

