15.1.4 Duration of Response

The criteria for overall response will be the time from randomization and first sign of local progression or development of metastatic disease.

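### Any tumor outside the pancreas counts as distant progression, so new direct extension of the primary enters metastasis-free survival and can be missed by local PFS

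*Combined protocol and SAP*

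**What the plan says.** All references are to the combined protocol and SAP.

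- **15.1.2, distant progression:** "Distant progression will be defined as any tumor found outside of the pancreas on CT scan". The sentence before it defines local progression differently, as at least 20% "increased size on follow-up CT scan as compared to baseline CT", and names that baseline as the last scan before chemotherapy.
- **15.1.3, metastatic disease:** "Any disease outside of the pancreas will be considered metastatic disease". Confirmation is optional: "If possible a biopsy should be obtained to confirm metastasis". The preceding sentence refers non-target lesions to standard radiographic criteria.
- **15.1.5, endpoints:** "Metastasis free survival will be the duration from randomization to metastasis or death from any cause". Local PFS ends at local progression or death, and PFS at documented progression or death. All are timed from randomization.
- **7.5, removal:** disease progression removes the patient from the study. After that, only overall survival is tracked.
- **3.1 and 3.2, population:** patients must be unresectable. The exclusion reads "Metastatic disease" and is not defined there.

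Some text limits the rule. Section 15.1 says "Initial follow-up scans post-treatment will be compared to the" pre-chemotherapy baseline scan. Section 15.1.4 speaks of the "first sign of local progression or development of metastatic disease". Section 15.1.6 provides independent radiology review of responses at study completion.

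**The concern.** The rule turns on one anatomical boundary, the edge of the pancreas. It does not ask whether a lesion is new, or whether it is separate from the primary. The protocol itself places these tumors against other organs: 6.1.1 puts fiducials in duodenum next to the tumor, and 6.1.3 foresees planning margins reaching duodenum or stomach. Section 2.2 lists gastric outlet obstruction among the consequences of local progression. Under 15.1.2 and 15.1.3, growth across that boundary is distant disease.

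Two secondary endpoints depend on keeping the categories apart. Section 2.3 gives SBRT two separate aims: better local control and, in theory, less distant seeding. If direct extension counts as metastasis, metastasis-free survival mixes the two, and a local-control effect could appear as a metastasis effect. Local PFS can lose failures that SBRT is meant to prevent. Because SBRT acts on the primary, the misfiling need not be equal in the two arms. Centers that follow the text and centers that use ordinary radiological judgment would also report different endpoints.

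**Working it through.** **Step 1. Apply the written definitions to possible CT findings after randomization.**

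| Finding | Distant (15.1.2, 15.1.3) | Local (15.1.2) | Metastasis-free survival | Local PFS | PFS |
|---|---|---|---|---|---|
| New separate lesion in another organ | yes | no | event | no event | event |
| New direct extension, growth at least 20% | yes | yes | event | event | event under either rule |
| New direct extension, growth below 20% | yes | no | event | no event | event through the distant rule only |
| Extension unchanged from baseline, 15.1 comparison applied | no | no | none | none | none |
| Extension unchanged from baseline, 15.1.2 read in isolation | yes | no | event | no event | event |

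Rows 2 and 3 carry the point. Both are correct comparisons with baseline, so the comparison rule in 15.1 does not remove them.

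**Step 2. Follow the row 3 patient in local PFS.** Distant progression triggers removal under 7.5, with survival follow-up only. A later local progression may never be imaged. By 15.1.5 the patient's local PFS time then runs to death or, if death is not observed, is censored at the last local evaluation. The actual local failure is recorded late or not at all.

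**Step 3. The 20% window.** Local growth is measured against the pre-chemotherapy scan. A patient with a partial response (30% decrease, 15.1.2) has a diameter of 0.70 of baseline. Reaching 1.20 of baseline takes 1.20 / 0.70 = 1.71, or 71% regrowth. Extension below the local threshold is therefore possible. How often it occurs is not in the documents.

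**Step 4. The plan's own design figures (17.3.2, 17.5.2) reproduce.** Inputs: 86 per arm, exponential medians 6 and 10.2 months, accrual A = 60, minimum follow-up F = 12, two-sided 0.05.

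- Hazard ratio = 6 / 10.2 = 0.588.
- Event probability = 1 − [exp(−λF) − exp(−λ(A+F))] / (λA), with λ = ln 2 / median.
- Expected events: 82.9 + 76.8 = 159.7 (plan: 83 + 77 = 160).
- Power at 160 events, Schoenfeld: Φ(√160 / 2 × |ln 0.588| − 1.96) = 91.9%.
- Power at 160 events, Freedman: Φ(√160 × (1 − 0.588) / (1 + 0.588) − 1.96) = 90.6% (plan: 91%).

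The design arithmetic is sound. A definition limited to new, non-contiguous lesions leaves these assumptions as they stand.

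**Step 5. Hypothetical worst case for PFS.** Assume a share q of both arms is called progressed at a 3-month scan, whatever the true status. Times are exponential with the plan's medians, T = min(T, 3) for affected patients, censoring is at 12 + U(0, 60) months, and the test is log-rank at two-sided 0.05. No section gives q.

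| q | Average HR (2000 replicates) | Power (2000 replicates) | Power (second run, 600 replicates) |
|---|---|---|---|
| 0% | 0.587 | 91.6% | 92.8% |
| 10% | 0.615 | 86.0% | 85.3% |
| 20% | 0.645 | 80.6% | 81.8% |
| 30% | 0.673 | 73.2% | 75.5% |

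Monte Carlo error is about 1 to 2 points. These figures show sensitivity to an assumption; they do not estimate what will happen in this trial.

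**The case against.** A reader might infer more: that stable extrapancreatic tumor already present at baseline becomes distant progression at the first follow-up CT, so that PFS fills with false early events and loses the power shown in step 5. The documents do not support that as the plan's meaning.

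- Section 15.1 compares initial follow-up scans with baseline, the defined term is progression, and 15.1.4 speaks of disease developing. Calling unchanged disease progression means setting all of this aside.
- Read literally, 15.1.3 together with 3.2 would already have excluded such patients. The power loss needs a lenient reading at entry and re-staging, then a literal one three months later, for every affected patient in both arms.
- The affected share is assumed. No section says how often these tumors extend beyond the pancreas.

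Two further objections limit the remaining point. Section 15.1.2 allows local and distant progression to be recorded together, so extension with at least 20% growth is not lost from local PFS and does not change PFS. How regional nodes are classed is a convention, and nothing in the plan favors one choice.

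These objections stand, but they do not dispose of rows 2 and 3. None of the limiting text says that a distant lesion must be non-contiguous. The reference to standard criteria is followed at once by the broad sentence, and the independent radiologist is given no other definition.

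**Conclusion.** The concern holds for endpoint classification. As written, new direct extension of the primary is an event in metastasis-free survival. When growth is below 20%, local PFS can miss it, because patients removed for progression are then followed for survival alone. This conclusion rests on the wording of 15.1.2, 15.1.3, 15.1.5 and 7.5 and needs no assumed rate.

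For PFS the effect is narrower. It arises only from extension below the 20% threshold, or from unchanged baseline disease read literally against 15.1. Its size and direction cannot be derived from the documents, and the power figures are a hypothetical worst case. The stated 160 events and 91% power are not in error.

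There is also an internal tension. If any disease outside the pancreas is metastatic, the exclusion in 3.2 bars every patient whose tumor extends past it, although the trial is for locally advanced disease. Sections 3.2 and 15.1.3 must be reconciled.

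**What to change.** - In 15.1.2 and 15.1.3, define distant progression as a lesion that is new relative to the named baseline CT and not contiguous with the primary.
- Class direct extension of the primary as local, counted only on growth or new appearance. Counting new appearance adds to the present size-only local rule, so the text should say so openly.
- State one convention for regional nodes and use it in both sections. The choice is the sponsor's.
- Reconcile the broad sentence in 15.1.3 with the metastatic-disease exclusion in 3.2, so that one meaning of metastatic applies at entry and at follow-up.
- Carry the same wording into progression recording and into the instructions for the independent review in 15.1.6.

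The cost is protocol wording, with no new scans or patients. The downside is that scans already read under the present wording need reclassifying.
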